| Primary Endpoints                                   | 
Primary Effectiveness Endpoint:
 
Technical success defined as complete coverage of the tumor as determined ≤36 hours post-index procedure by magnetic resonance imaging (MRI) or computerized tomography (CT). [Core Lab Adjudicated]
 
Primary Safety Endpoint:
 
Freedom from index procedure related major complications, defined by Clavien-Dindo Classification Grade 3 or higher up to 30 days after the last histotripsy procedure. [Clinical Events Committee Adjudicated]
  |
| Secondary Endpoints                                 | 
 
1. Technique efficacy (primary) defined as the percentage of targeted tumors successfully eradicated post-index procedure assessed via MRI or CT at 90-days post-index procedure without repeat Histotripsy [Core Lab Adjudicated]
 
2. Technique efficacy (secondary) defined as the percentage of targeted tumors successfully eradicated post-index procedure assessed via MRI or CT at 90-days post-index procedure after repeat Histotripsy [Core Lab Adjudicated]
 
   |
| Follow-Up Visits                                    | All treated subjects will have a 14-day, 30-day, 90-day, and 180-day follow up assessment or until the trial is closed, whichever comes first.   |
| General Inclusion                                   | Subjects are eligible for the trial if all the following criteria are met:  |

|                          |  |
|--------------------------|--|

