| Imaging Inclusion | 
 
10. The tumor selected for histotripsy treatment must be <math>\leq 3</math>cm in longest diameter.
 
11. Subject has an adequate acoustic window to visualize targeted tumor using the HistoSonics Investigational System.
 
12. Subject will undergo histotripsy treatment of only one (1) tumor during the index procedure, regardless of how many tumors the subject has.
 
  |
| General Exclusion | 
Subjects are not eligible for participation in the trial if any of the following criteria are met:
 
 
1. Subject is pregnant or planning to become pregnant or nursing (lactating) during the trial period.
 
2. Subject is enrolled and being actively treated in another investigational pharmaceutical or device trial <math>\leq 30</math> days prior to planned index procedure date.
 
   |

|  |   |
|--|---|

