|  | 

3. Subject is undergoing active chemotherapy for any cancer ≤14 days prior to planned index procedure date.

4. Subject is undergoing active immunotherapy ≤40 days prior to planned index procedure date.

5. In the Investigator's opinion, the subject has co-morbid disease(s) or condition(s) that would cause undue risk and preclude safe use of the HistoSonics Investigational System.

6. Subject is on dialysis or being considered for dialysis.

7. Subject has not recovered to Common Terminology Criteria for Adverse Events (CTCAE) grade 2 or better from any adverse effects (except alopecia and neuropathy) related to previous anti-cancer therapy.

8. Subject has an uncorrectable coagulopathy other than that induced by aspirin or non-steroidal anti-inflammatory drugs.

9. Subject has a planned cancer treatment (e.g., nephrectomy, chemotherapy, immunotherapy etc.) prior to completion of the 30-day follow-up visit.

10. Subject has had previous treatments with chemotherapy, radiotherapy, or both that have not been discontinued ≥14 days prior to the planned index procedure date and have not recovered (CTCAE grade 2 or better) from related toxicity (exclusive of alopecia and neuropathy).

11. Subject has previous treatment with immunotherapies that has not been discontinued ≥40-days prior to the planned index procedure date and has not recovered from related toxicity (CTCAE grade 2 or better).

12. Subject has a life expectancy less than one (< 1) year.

13. In the investigator's opinion, histotripsy is not a treatment option for the subject.

14. Subject has a concurrent condition that could jeopardize the safety of the subject or compliance with the protocol.

15. Subjects' targeted tumor has had prior locoregional therapy (e.g., ablation, embolization, radiation).

16. Subjects' tumor is not treatable by the HistoSonics Investigational System's working ranges (refer to User Guide).

17. In the physician's opinion, the anticipated risk of intervention outweighs the potential benefits of the intervention.

18. Subject has acute renal failure.

19. Subject has a genetic predisposition to kidney cancer such as:

• Von Hippel Lindau (VHL)

• Hereditary Papillary Renal Carcinoma (HPRC)

• Birt-Hogg-Dubé Syndrome (BHD)

• Tuberous Sclerosis Complex (TSC)

• Hereditary Leiomyomata's Renal Cell Carcinoma (HLRCC)

• Reed's Syndrome

 |

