|--|---|

|                            |  |
|----------------------------|--|
|                            | 

• Succinate Dehydrogenase B Deficiency (SDHB)

• BRCA 1 associated protein -1 (BAP1) Renal Cell Carcinoma

• MITF predisposed Renal Cell Carcinoma

 
20. Tumor is an angiomyolipoma.
 
21. Subject has a known sensitivity to contrast media and cannot be adequately pre-medicated.
   |
| Imaging Exclusion   | 
22. The targeted tumor is not clearly visible with diagnostic ultrasound and either magnetic resonance imaging (MRI) or computerized tomography (CT).
 
23. Targeted tumor with adequate margin overlaps the renal pelvis, main renal vessel, ureter, or other vital structure.
 
24. Targeted tumor with adequate margin overlaps a non-targeted tumor visible via imaging.
 
25. The treatment of the tumor will not allow for an adequate margin as determined by the investigator.
 |
| Statistical Methods | All endpoints will be summarized descriptively with 95% (Wilson) confidence intervals. As a pilot trial, no formal hypotheses will be defined; the endpoints are designed to provide additional information for the development of a pivotal trial.  |
| Sponsor             | HistoSonics, Inc.
[name]
[name]
United States of America (USA)
[contact]   |

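### Does the synopsis need a rule for targets that receive other cancer treatment before the 90-day technique efficacy scan?

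*Combined protocol and SAP*

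**What the plan says.** All references are to the CAIN protocol synopsis.

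- **General Exclusion, item 9** excludes a candidate if the "Subject has a planned cancer treatment (e.g., nephrectomy, chemotherapy, immunotherapy etc.) prior to completion of the 30-day follow-up visit". It looks at what is planned at entry.
- **Secondary Endpoints, items 1 and 2** both measure "the percentage of targeted tumors successfully eradicated post-index procedure", with core-lab adjudication. Item 1 is "assessed via MRI or CT at 90-days post-index procedure without repeat Histotripsy". Item 2 is "assessed via MRI or CT at 90-days post-index procedure after repeat Histotripsy".
- **Primary Effectiveness Endpoint** is "complete coverage of the tumor as determined ≤36 hours post-index procedure", so treatment given weeks later cannot affect it.
- **Imaging Inclusion, item 12** limits the index procedure to one tumor, "regardless of how many tumors the subject has". With at most 20 subjects (Enrollment), there are at most 20 index targets.
- **Statistical Methods** states: "All endpoints will be summarized descriptively with 95% (Wilson) confidence intervals". The same row says that the trial, as a pilot, tests no hypothesis. It gives no rule on analysis populations, missing readings or intervening treatment.

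**The concern.** The two horizons appear not to meet. A subject could enter with nephrectomy or systemic therapy planned for after the 30-day visit, or could receive such treatment because histotripsy worked poorly. Either way, the 90-day scan of that target is hard to use: a resected tumor cannot be read, and a tumor under other therapy gives a reading that histotripsy alone did not produce.

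The sponsor evidently saw that intervening treatment changes what the scan means, since it wrote separate endpoints without and after repeat histotripsy. Other treatment is not mentioned. Such a target could be scored as a failure, dropped, or scored as eradicated. If failures are the ones treated, the last two choices inflate the rate. With so few targets each one matters, and the stated objective is to inform a pivotal trial.

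**Working it through.** The plan gives no assumed eradication rate, no rate of other treatment and no sample-size derivation, so there is no figure to reproduce. The check has two parts.

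**1. Do the passages conflict?** Item 9 governs eligibility and speaks only of treatment planned at entry. The endpoints govern measurement. Item 9 would not prevent unplanned treatment after a poor result, before or after day 30, so moving its horizon would not close the counting gap. Its 30 days are also close to the primary safety window, which runs to 30 days after the last histotripsy procedure. The passages do not contradict each other. What remains is an unstated convention.

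**2. How much could the convention move the estimate?** Assumed: 20 targets, 14 truly eradicated (70%, Wilson 48.1 to 85.5%). Of these 20, *k* receive other treatment before the 90-day scan, and *f* of those *k* are true failures. Then:

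- counted as failures: (14 − (k − f)) / 20
- dropped: (14 − (k − f)) / (20 − k)
- read as eradicated: (14 + f) / 20

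| k | f | Counted as failures | Dropped | Read as eradicated |
|---|---|---|---|---|
| 1 | 1 | 14/20 = 70.0% | 14/19 = 73.7% | 15/20 = 75.0% |
| 3 | 0 | 11/20 = 55.0% | 11/17 = 64.7% | 14/20 = 70.0% |
| 3 | 3 | 14/20 = 70.0% | 14/17 = 82.4% | 17/20 = 85.0% |
| 4 | 0 | 10/20 = 50.0% | 10/16 = 62.5% | 14/20 = 70.0% |
| 4 | 4 | 14/20 = 70.0% | 14/16 = 87.5% | 18/20 = 90.0% |

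If treatment is unrelated to outcome, the expected *f* at k = 3 is 3 × 6/20 = 0.9, so k − f = 2.1. The expected results are:

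- counted as failures: (14 − 2.1)/20 = 11.9/20 = 59.5%
- dropped: 11.9/17 = 70.0%
- read as eradicated: 14.9/20 = 74.5%

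The preferable convention therefore depends on why treatment was given. When failures are the ones treated, counting as failures is exact and dropping overstates. When treatment is unrelated to outcome, dropping is unbiased and counting as failures is 10.5 points too low, the largest error of the three. Treatment already planned at entry, which is all that item 9 concerns, is the case most plausibly unrelated to the histotripsy result.

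**The case for a change.** The strongest argument for a change is that in a trial without hypothesis tests the estimates are the product, and these two endpoints are the only listed ones that measure eradication. Each target moves the rate by 1/20 = 5 points between the success and failure conventions, and the Wilson interval does not reflect that choice. A convention chosen after results are seen can be chosen to flatter. Writing one down costs a few sentences.

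Much of this stands. The synopsis is silent, the arithmetic is right, and a convention fixed in advance is better than one chosen later. Three things weaken it as a call for change:

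- A synopsis with a two-sentence statistical row is not where such a rule would be expected. Its absence here says little about the full protocol.
- The reading is less open than it seems. A percentage of targeted tumors keeps every target in the denominator, so dropping one departs from the wording. Crediting a surgeon's resection to histotripsy would defeat the purpose of a technique efficacy measure, and a core lab would be likely to notice a resected target. Systemic therapy is less visible on a scan, and there the ambiguity is greater.
- The specific remedy, counting every locally treated target as a failure, replaces one possible bias with another, as the 59.5% shows. The fallback of using the last scan before treatment is weak, because the only earlier core-lab scan named is the one at 36 hours or less, which shows coverage and not eradication.

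**Conclusion.** No change to the plan follows. The synopsis leaves a convention unwritten; it does not state one that gives a wrong result. Item 9 and the 90-day endpoints need no reconciling.

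Under the assumed 14 of 20, one failed target treated by other means moves the estimate by 3.7 points (dropped) or 5 points (read as eradicated). The Wilson interval for 14/20 extends 21.9 points below and 15.5 points above the estimate. Shifts of 17.5 to 20 points need four of 20 targets treated, all with the same true outcome, and nothing in the documents suggests that frequency. Both primary endpoints are untouched, and no threshold or decision rule depends on the secondary ones.

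A sensible analyst would keep all targeted tumors in the denominator, list the number, timing and reason of any other treatment before the 90-day scan, and show the rate with those targets counted as failures and excluded. With at most 20 targets, a reader can then see the effect of the choice directly. This conclusion rests on such treatments being few and being reported. It would be worth confirming that the full protocol or SAP states the convention.
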